3.3.4. FIX Antigen Levels and Coagulation Activation Tests

FIX antigen will be assessed in parallel with FIX:C and follows the same rule that any sample taken within 7 days after(14 days if Extended half-life [EHL] product is used) of exogenous FIX replacement therapy administered for any purpose (including treatment of bleeding, preventive purpose, or resumption of FIX prophylaxis regimen) will be excluded from the analysis of FIX antigen. The assessment value of FIX antigen will be summarized.

Coagulation activation tests are: activated partial thromboplastin time (aPTT), international normalized ratio (INR), D-dimer, thrombin generation assay (TGA), thrombin-antithrombin level (TAT). The tests will be conducted at baseline, post-baseline and as clinically indicated throughout the study.

3.4. Baseline Variables and Covariates

Baseline definition for each relevant endpoint is defined in the above section, as needed.

Baseline characteristic will be summarized and will include Age group (cut-off <35, or \geq 35 years), and Region (North America, Europe, Asia/Pacific, and South America).

3.5. Safety Endpoints

The safety endpoints of this study include vital signs, electrocardiogram (ECG), adverse events (AEs), serious AEs (SAEs), physical examination findings, laboratory test results, surgery information and liver ultrasound findings.

3.5.1. Adverse Events

The summary tables of AE will be based on data collection presented in Figure 2 below. The time period for actively eliciting and collecting AEs and SAEs ("active collection period") for each participant begins from the time the participant provides informed consent, which is obtained before the participant's participation in the study (i.e., before undergoing any study-related procedure and/or receiving PF-06838435), through and including 6 years after the last administration of the PF-06838435, or at End of Study (EOS) for participants who discontinue. The active collection period for this study is categorized into Short Term (up to and including 52 weeks post PF-06838435 infusion). The Long-Term Monitoring Period is defined as Week 53 post PF-06838435 infusion until EOS.

[figure not shown]
During the Short Term Monitoring Period, all SAEs (including medically important events (MIE), see protocol Appendix 3) and all non-serious AEs will be collected.

[figure not shown]
During the Long-Term Monitoring Period the following adverse events will be collected:

- SAEs (including MIEs, see protocol Appendix 3);
- Non-serious AEs determined to be related to PF-06838435 by the investigator or where causality is unknown;

Adverse Events of Special Interest (AESIs), as detailed in protocol Appendix 3, will be summarized. There is no lag time specified for adverse event reporting in this study.

Treatment emergent adverse events (TEAEs) include any adverse events that occur on or after the infusion of PF-06838435. Missing severity will be not imputed. AEs will be coded using the version of Medical Dictionary for Regulatory Activities (MedDRA) available at the time of database release and summarized by system organ class and preferred term.

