### 8.3.9. Adverse Events of Special Interest

All AESIs must be reported as an AE or SAE following procedures described in [Section 8.3.1](#) through [8.3.4](#). An AESI is to be recorded as an AE or SAE on the CRF. In addition, an AESI that is also an SAE must be reported using the CT SAE Report Form.

Adverse events of special interest include: all medically important events (see [Appendix 3](#)) that are to be reported as an SAE, and any clinical thrombotic event or hypersensitivity events assessed as non-serious AEs.

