**e. Is a congenital anomaly/birth defect**

**f. Other situations:**

- Medical or scientific judgment should be exercised in deciding whether SAE reporting is appropriate in other situations such as important medical events that may not be immediately life-threatening or result in death or hospitalization but may jeopardize the participant or may require medical or surgical intervention to prevent one of the other outcomes listed in the above definition. These events should usually be considered serious.

Examples of such events include invasive or malignant cancers, intensive treatment in an emergency room or at home for allergic bronchospasm, blood dyscrasias or convulsions that do not result in hospitalization, or development of drug dependency or drug abuse.

- Suspected transmission via a Pfizer product of an infectious agent, pathogenic or non-pathogenic, is considered serious. The event may be suspected from clinical symptoms or laboratory findings indicating an infection in a participant exposed to a Pfizer product. The terms "suspected transmission" and "transmission" are considered synonymous. These cases are considered unexpected and handled as serious expedited cases by pharmacovigilance personnel. Such cases are also considered for reporting as product defects, if appropriate.
- In this study, the following events that occur post-study treatment infusion are considered medically important events and should be reported as SAEs:
  1. Any participant develops clinical thrombotic event (with the exception of IV infusion-site thrombophlebitis).
  2. Any participant develops FIX inhibitor as assessed by Nijmegen assay ( $\geq 0.6$  Bu/mL, central laboratory).

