**A SAE is defined as any untoward medical occurrence that, at any dose:**

3. Any participant develops hypersensitivity reaction (eg, bronchospasm and anaphylaxis). Infusion site reactions should be reported as serious only if they meet serious criteria.
4. Any participant develops a hepatic malignancy.
5. Any participant develops drug-related elevated hepatic transaminases that fail to improve or resolve through treatment with immunosuppressive regimens.
6. Any occurrence of a malignancy assessed as having reasonable possibility of being related to study drug.

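### Protocol 8.3.9 and Appendix 3 disagree on whether post-infusion thrombotic and hypersensitivity events can be non-serious, and SAP 3.5.1 takes its AESIs from the narrower of the two

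*SAP*

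**What the plan says.** Four places bear on the definition.

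- **Protocol 8.3.9** defines AESIs in two parts. The first is the medically important events of Appendix 3 that are reported as SAEs. The second is "any clinical thrombotic event or hypersensitivity events assessed as non-serious AEs". On expedited reporting it says that "an AESI that is also an SAE must be reported using the CT SAE Report Form". Protocol 8.3 sends the reader to this section for the AESI definition.
- **Protocol Appendix 3 (10.3.2)** gives six post-infusion events that "are considered medically important events and should be reported as SAEs". Item 1 reads "Any participant develops clinical thrombotic event (with the exception of IV infusion-site thrombophlebitis"). Item 3 reads "Any participant develops hypersensitivity reaction (eg, bronchospasm and anaphylaxis). Infusion site reactions should be reported as serious only if they meet serious criteria". Nothing in the appendix carries the label AESI.
- **SAP 3.5.1** states "Adverse Events of Special Interest (AESIs), as detailed in protocol Appendix 3, will be summarized" and does not mention Protocol 8.3.9.
- **SAP 2.1 and Protocol Section 3** each print six AESI types, including hypersensitivity reactions and clinical thrombotic events. Neither attaches a seriousness condition or an infusion-site exception.

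Two further rules set the consequences. Under Protocol 8.3.1.1 and the tables in 10.3.3, every SAE goes to the sponsor's safety group within 24 hours and no non-serious AE does. Under Protocol 8.3.1, repeated in SAP 3.5.1, non-serious AEs from Week 53 onward are collected only when related to the product or of unknown causality.

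**The concern.** Read literally, Appendix 3 makes any post-infusion clinical thrombotic event or hypersensitivity reaction away from the infusion site an SAE. Section 8.3.9 provides for events of the same two kinds to be assessed as non-serious and does not confine that provision to the appendix's exceptions. A site with a mild systemic hypersensitivity reaction cannot tell from the text whether a non-serious assessment is open to it.

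The classification matters because it decides whether the event is expedited and, in the long-term period, whether an event also judged unrelated is recorded. The SAP adds a second difficulty: for its AESI summary it cites the document that lacks the non-serious part of the definition. These are two named risks in a small single-arm gene-therapy study, so the AESI table should rest on one stated definition.

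**Working it through.** The plan gives no figure on this point to reproduce. The check sets the definitions side by side and follows an event through each rule.

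**Where the definitions differ**

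| Source | Can a thrombotic or hypersensitivity event be non-serious? | Infusion-site exception |
|---|---|---|
| Protocol 8.3.9 | Yes, in the second part of the definition | None stated |
| Protocol 10.3.2 | Not if post-infusion, except at the infusion site | Thrombophlebitis; reactions not meeting serious criteria |
| Protocol Section 3 and SAP 2.1 | Not addressed | None stated |
| SAP 3.5.1 | Takes over Appendix 3 | Takes over Appendix 3 |

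**Following an event through the rules**

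1. *Post-infusion, away from the infusion site, handled under Appendix 3.* It is an SAE with a 24-hour report, is collected throughout the study, and is an AESI under every source.
2. *The same event assessed as non-serious under 8.3.9, up to Week 52.* It is recorded on the CRF with no 24-hour report. Its type still matches the Appendix 3 item and the SAP 2.1 list, so it belongs in the AESI table unless the programmer treats the Appendix 3 list as an SAE filter. SAP 6.6.1 states no such filter and names AESIs as a category separate from serious AEs.
3. *The same event assessed as non-serious from Week 53.* If related or of unknown causality, it is collected and handled as in 2. If unrelated, 8.3.1 does not collect it, so no table can show it. The collection rule causes that loss, but the event comes under the rule only because 8.3.9 admits a non-serious assessment.
4. *Infusion-site thrombophlebitis, or non-serious hypersensitivity at the infusion site.* There is no 24-hour report under either section, so reporting is not in conflict. Appendix 3 excludes these events. Its wording for item 1 treats the thrombophlebitis as an exception to the class of clinical thrombotic events, which implies that it would otherwise belong there. Section 8.3.9 has no such exception and can count both as AESIs. A table built strictly from the SAP 3.5.1 pointer could leave them out, while one built from the SAP 2.1 types could include them.

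**How much follow-up the collection question covers**

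The study lasts 312 weeks, of which 52 are the short-term period. The long-term period is 312 − 52 = 260 weeks, or 260/312 = 83% of planned follow-up.

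**The case against.** The strongest reply is that the sections can largely be read together. Appendix 3 covers only events after the infusion of study treatment and excepts certain infusion-site events, whereas AE collection starts at consent. The non-serious part of 8.3.9 therefore has something to apply to: pre-infusion events and the infusion-site exceptions. Section 8.3.9 also cites Appendix 3 and routes reporting through 8.3.1 to 8.3.4, so a site that reads it is sent to the SAE rule. The six AESI types in SAP 2.1 match the six Appendix 3 items one for one, so the SAP's pointer leads to a recognisable list even without the label.

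Much of this stands. It shows that the two definitions do not collide on every event. It does not settle the matter, because 8.3.9 nowhere says that its non-serious part is limited to events outside Appendix 3. The harmonising reading is possible but has to be supplied by the reader.

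A reader might also infer that all thrombotic and hypersensitivity events judged non-serious would drop out of the AESI table. The documents do not support that. SAP 2.1 and Protocol Section 3 list the types without regard to seriousness, and SAP 6.6.1 applies no SAE filter. SAP 6.6.1 also tabulates all first-year AEs by system organ class and preferred term, so an event recorded in that year would appear there in any case.

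**Conclusion.** This is an internal inconsistency in the safety definitions, with three parts:

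- **Seriousness.** For post-infusion clinical thrombotic and hypersensitivity events other than the infusion-site exceptions, the protocol does not say consistently whether a non-serious assessment is possible. The 24-hour report depends on the answer.
- **Collection after Week 52.** For such an event also judged unrelated, the same ambiguity decides whether it is collected at all, over 260 of 312 planned weeks.
- **Tabulation.** SAP 3.5.1 points to a list that omits the non-serious part of 8.3.9. The likely loss is confined to infusion-site events, or to an SAE-only reading that the SAP does not state.

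The number of events affected cannot be derived from the documents. A reader might divide one participant by the planned 40 and quote 2.5 percentage points. That is only the weight of one participant. It does not estimate how many would be misclassified or omitted, and the number dosed may exceed 40. No efficacy hypothesis, error rate or sample size is affected. The conclusion assumes that sites and programmers work from the wording as printed. It takes no position on which reporting rule is right.

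**What to change.** 1. In SAP 3.5.1, replace the reference to Appendix 3 with Protocol 8.3.9, and check that the list in SAP 2.1 agrees with it, including on infusion-site events.
2. State in the SAP that AESIs are selected by event type regardless of seriousness, and show serious and non-serious events separately in the AESI table.
3. Reconcile Protocol 8.3.9 with 10.3.2, so that the protocol says once whether these post-infusion events can be assessed as non-serious. If the non-serious part of 8.3.9 is meant only for events outside the Appendix 3 list, say so there. The sponsor has to decide which rule applies.
4. In the same place, state what follows for collection after Week 52, since 8.3.9 requires all AESIs to be reported while 8.3.1 limits which non-serious events are collected.

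The cost is one SAP cross-reference, one SAP sentence, a split in one table and a short protocol clarification. The SAP changes should be made before database lock. They cannot recover events that were never collected, so the protocol clarification should not wait for the analysis.

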3.5.2. Laboratory Data

Safety laboratory data collected in this study include:

- Hematology: white blood cell (WBC) and differential, red blood cell (RBC), hemoglobin, hematocrit, and platelet count;
- ABO blood group (at Screening if unknown);
- Chemistry: Na, K, Cl, phosphate, bicarbonate, glucose, blood urea nitrogen (BUN), serum creatinine.

Certain selected lab tests will only be conducted at screening, and again if clinically indicated. For example:

- Hepatitis: hepatitis B surface antigen (HBsAg), hepatitis B core antibody (HBcAb), hepatitis B virus (HBV)- deoxyribonucleic acid (DNA); hepatitis C virus (HCV)-Ribonucleic acid (RNA) Quantitative, HCV viral load (if indicated);
- Liver fibrosis: FibroScan, FibroTest/FibroSURE, AST to platelet ratio index (APRI);
- human immunodeficiency virus (HIV): Antibody testing, and CD4 count/HIV viral load (if antibody positive);
- Urinalysis: pH, specific gravity, protein, blood, ketones, glucose.

Liver function tests:

Some study-specific laboratory test results, such as , α -Fetoprotein and liver function test (LFT) are to be collected. Elevations in Alanine transaminase (ALT)/ Aspartate transaminase (AST) (with associated ELISPOT data) and/or steroid therapy will be identified and reported.

The baseline assessment is based on the latest evaluation prior to or on the day of PF-06838435 infusion.

3.5.3. Vital Signs and Other Safety Endpoints

Vital signs, electrocardiograms (PR, QRS, QT, and corrected QT intervals (QTc)) measurements and abnormality, abnormal finding from physical examination will be summarized.

3.5.4. Concomitant Medication

Any concomitant therapy throughout the study will be collected as follows:

- All concomitant therapy during the Short-Term Monitoring Period (up to and including 52 weeks post PF-06838435 infusion);
- The concomitant therapy associated with adverse events (AEs) to be reported during the Long-Term Monitoring Period (Week 53 post PF-06838435 infusion until EOS).

Concomitant medication will be coded, and missing data will be handled per Pfizer data reporting standard.

3.5.5. Liver Ultrasound

All participants will undergo ultrasound imaging of the liver at times specified in the SoA.

4. ANALYSIS SETS (POPULATIONS FOR ANALYSIS)

This study is an open-label, single-arm study. The populations for analyses are outlined in the table below.

Population	Description
Enrolled	All participants who sign the informed consent form (ICF) and meet all inclusion/exclusion criteria
Dosed	All participants enrolled in the study and who received PF-06838435 infusion
Safety	All participants enrolled in the study and who received PF-06838435 infusion, which is the same as dosed population.
Evaluable	All participants enrolled in the study and who received PF-06838435 infusion and have no significant interruption of efficacy measurement.

The Evaluable analysis population listed above would exclude participants with significant interruption of efficacy measurement, or participants who do not have or have not yet completed 15 months of follow up post PF-06838435 infusion. Significant interruption will be assessed after discussion between the investigator and the medical monitor, e.g., if a participant requires a major surgery, this will be a significant interruption of measurement.

In this study, there are also substudies planned, for which the analysis populations are outlined below.

X-ray Substudy	All dosed participants sign the additional ICF for the X-ray substudy and meet all
Analysis Population	inclusion/exclusion criteria, and the participant's joint images have been
	reviewed.
MRI Substudy	All dosed participants who are dosed and sign the additional ICF for the MRI
Analysis Population	substudy and meet all inclusion/exclusion criteria, and the participant's joint
	images have been reviewed following the extended MRI scale with a final score
	combining soft-tissue and osteochondral sub-scores at baseline, and any data
	post-baseline
Vector Shedding	All dosed participants who sign the additional ICF for the Vector Shedding
Substudy Analysis	substudy and meet all inclusion/exclusion criteria, and who have any additional
Population	vector shedding data

5. GENERAL METHODOLOGY AND CONVENTIONS

The primary analysis is planned when 40 participants have completed 15 months of follow up after infusion of PF-06838435. The final analysis will be conducted when all dosed participants have completed the entire study (planned 6 years in duration per participant)/or discontinued. There may be several periodic reviews of data between primary analysis and final analysis for the purpose of publications and regulatory updates, etc.

The planned primary analysis is focused on the data collected during the first 15 months post infusion of PF-06838435. Unless otherwise specified analyses will be performed on the Dosed population and will include available data from the time of infusion (or Week 12 as appropriate) through 15 months post infusion regardless of the length of follow up. The final analysis will analyze extended efficacy and longer-term safety and will be performed once all participants have been followed for 6 years or have otherwise withdrawn from study. The endpoint assessments at the specific time points are listed in the table below.

En	dpoint	Primary analysis Statistical Analysis				
•	Primary	ABR for total bleeds (treated and untreated, from Week 12 to Month 15)				
٠	Secondary	ABR for treated bleeds from Week 12 to Month 15				
		AIR for FIX infusions from Week 12 to Month 15				
		Actual value of FIX:C by study visit and the geometric mean of FIX:C from Week 12 to Month 15				
		FIX consumption, from Week 12 to Month 15				
		Number of bleeding events of specific type from Week 12 to Month 15: spontaneous, traumatic; and untreated bleeding.				
		Frequency of target joint bleeds, from Week 12 to Month 15				
		Percentage of participants without bleeds (total bleeds and treated bleeds) will be summarized from Week 12 to Month 15.				
		HJHS at 12 months post PF-06838435 infusion				
		Haem-A-QoL Physical Health domain and HAL Complex Lower Extremity Activities component score at 12 months post PF-06838435 infusion				

		Short-term safety				
• Exp	oloratory	Haem-A-QoL (domains not previously specified) HAL (scores not previously specified) HLIQ item scores at 12 months EQ-5D-5L index score and visual analog scale at 12 months Correlation of FIX:C between one-stage assays and chromogenic straight assay				
		Vector Shedding Substudy				
• Exp	oloratory	A subset of participants will have more extensive vector shedding analysis performed on their specimens to further characterize the kinetics of vector shedding.				
		Final analysis				
• Secondary		ABR for total bleeds (treated and untreated) from Month 15 to Month 24, by yearly intervals after first 24 months and across 6 years of follow up Annualized bleeding rate for treated bleeds from Month 15 to Month 24, by yearly intervals after first 24 months and across 6 years of follow up Annualized infusion rate from Month 15 to Month 24, by yearly intervals after first 2 months and across 6 years of follow up Actual value of FIX:C by study visit and the geometric mean of FIX:C from Month 15 to Month 24, by yearly intervals after first 24 months and across 6 years of follow up Annualized FIX consumption from Month 15 to Month 24, by yearly after first 24 months and across 6 years of follow up Number of bleeding events of specific type from Month 15 to Month 24, by yearly intervals after first 24 months and across 6 years of follow up Number of bleeding events of specific type from Month 15 to Month 24, by yearly intervals after first 24 months and across 6 years of follow up: spontaneous and traumatic, and untreated bleeding. Frequency of target joint bleeds from Month 15 to Month 24, by yearly after first 24 months and across 6 years of follow up HJHS yearly after first 12 months through 6 years of follow up Haem-A-QoL Physical Health domain and HAL Complex Lower Extremity Activitie component score yearly after the first 12 months through 6 years of follow up				
• Exp	oloratory	 Haem-A-QoL (domains not previously specified) HAL (scores not previously specified) HLIQ item score yearly after the first 12 months through 6 years of follow up EQ-5D-5L index score and visual analog scale yearly after 12 months through 6 years of follow up Correlation of FIX:C between one-stage assays and chromogenic straight assay 				
_		X-ray Substudy				
• Exp	oloratory	Joint images will be reviewed and overall score, the score at specific joint, and target joint will be derived at year 3 and after 6 years of follow up. MRI Substudy				

•	Joint images will be reviewed following the extended MRI scale with a final score combining soft-tissue and osteochondral sub-scores (at year 3 and after 6 years of follow up).				
	Vector Shedding Substudy				
•	Exploratory	A subset of participants will have more extensive vector shedding analysis performed on their specimens to further characterize the kinetics of vector shedding.			

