## 9.2. Sample Size Determination

Participants who complete the lead-in protocol C0371004 will be screened to achieve desired sample size of 40 participants, and eligible participants will be assigned to study intervention. All 40 participants are expected to be evaluable in this one-armed study.

When all 40 participants have completed at least 15 months of follow-up post-infusion of PF-06838435, the  $ABR_{total}$  data will provide at least 90% power (one-sided test with  $\alpha=0.025$ ) to demonstrate non-inferiority of gene therapy compared to prophylaxis treatment on the difference in  $ABR_{total}$ , using a repeated measure negative binomial regression, with a non-inferiority margin of 3.0 bleeds/year. The assumed background rate of annualized bleeding is a conservative 5.0 and the assumed annualized bleeding rate post-PF-06838435 is 1.5. The details of non-inferiority margin selection are included in [Appendix 10](#).

The number of participants may exceed 40, because all participants who complete the lead-in study (C0371004) and meet other eligibility criteria will be allowed to participate in this study.

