6.2.2.2. Sensitivity/Supplementary Analysis

Percentage of the participants without exogenous FIX infusions will be defined in the overall time period after PF-06838435 infusion, the running total time period (i.e., Week 12 to Month 15, Week 12 to Year 2, Week 12 to Year 3, etc.) and with the same time periods as ABR such as Month 15, Year 2 (Month 15 to Month 24), Year 3, Year 4, Year 5 and Year 6. Descriptive statistics will include the total number of participants, frequencies and percentages of participants who have/have no infusions. The Dosed population will be used for this analysis.

Three sensitivity analyses will be performed:

1. comparing the AIR from Week 12 to Month 15 to the AIR collected during C0371004

2. comparing to the AIR during the most recent 6 months prior to infusion.

3. AIR during first 15 months post PF-06388435 infusion will be analyzed similarly as AIR from Week 12 to Month 15.

These analyses will be conducted on Dosed population.

The percentage of the participants who resume a FIX prophylaxis regimen will be determined for the overall time period, as well as for each time interval (from Week 12 to Month 15, Month 15 to Month 24, Year 3, Year 4, Year 5 and Year 6).

If there are a sufficient number (i.e., >20%, which is around 8 at the time of the final analysis) of participants who resume a FIX prophylaxis regimen, then the time to resumption of a prophylaxis regimen will be summarized.

AIR Year 2 (Month 15 to Month 24), Year 3, Year 4, Year 5 and Year 6, as well as AIR through the overall follow up will be tested using the same method to demonstrate superiority over AIR of SOC FIX prophylaxis regimen as secondary endpoints.

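### If more than 40 participants are dosed, the Week 12 to Month 15 yes/no percentages at the primary analysis include participants who have not completed the window, which shifts them in the product's favour

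*SAP*

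**What the plan says.** The timing and the analysis set come from different rules.

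- **Trigger (SAP Section 5):** "The primary analysis is planned when 40 participants have completed 15 months of follow up after infusion of PF-06838435".
- **Number dosed (Protocol 9.2):** "The number of participants may exceed 40, because all participants who complete the lead-in study (C0371004) and meet other eligibility criteria" may take part. No cap is given.
- **Analysis set (SAP Section 4):** Dosed is "All participants enrolled in the study and who received PF-06838435 infusion". Unless otherwise specified, SAP Section 5 applies this set to "available data from the time of infusion (or Week 12 as appropriate) through 15 months post infusion regardless of the length of follow up".
- **Infusion-free percentage (SAP 6.2.2.2, Dosed population):** "Descriptive statistics will include the total number of participants, frequencies and percentages of participants who have/have no infusions".
- **Resumption (SAP 6.2.2.2):** the percentage of "participants who resume a FIX prophylaxis regimen will be determined for the overall time period, as well as for each time interval", the first interval being Week 12 to Month 15. Time to resumption is summarised only if more than 20% resume.
- **Bleed-free percentage (SAP 3.2.6 and 6.2.6):** numbers and percentages with and without bleeding in the same window, on the Dosed population. It is a listed secondary endpoint in SAP Section 5.

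For ABR and AIR, SAP 3.1.1 and 3.2.2 say what to do with a participant not yet followed for the whole period: annualise what is available. No corresponding rule is given for the three percentages.

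**The concern.** A participant dosed beyond the first 40 may be only part-way through Day 82 to Day 469 at the data cutoff. If he has had no bleed, no infusion and no resumption so far, a plain split of the Dosed population puts him with those who went the full 388 days without one. If he has already had the event, he is counted correctly. So for participants still in the window the error runs one way, towards the product, and grows with the number dosed beyond 40.

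These are easily quoted figures from an open-label, single-arm trial. If resumption stays at or below 20%, its crude percentage is the only planned summary of how often it happens.

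**Working it through.** **Figures in the plan.** The window is 469 − 82 + 1 = 388 days, or 388/365.25 = 1.062 years. SAP 6.2.2.2 equates more than 20% resuming with around 8 participants: 0.20 × 40 = 8, which presumes a total of 40. No accrual schedule or expected total above 40 is given, so everything below is a range under stated assumptions.

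**Share not at Month 15.** With N dosed and 40 at Month 15, the share is (N − 40)/N: 44 dosed, 9%; 45, 11%; 48, 17%; 50, 20%.

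**Infusion-free percentage.** Let p be the true full-window percentage and p̄ the average percentage event-free so far among the other N − 40. Then

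shown = [40p + (N − 40)p̄]/N, and shift = (N − 40)(p̄ − p)/N.

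Assumptions: follow-up of the extra participants is uniform on 0 to 455 days, only time after Day 82 counts, and episodes requiring infusion occur at 0.5 to 1.5 per year. The event-free probability over time t is exp(−rate·t) (Poisson) or (1 + k·rate·t)^(−1/k) (negative binomial, dispersion k).

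| Model | p | p̄ | Shift, 45 dosed | Shift, 50 dosed |
|---|---|---|---|---|
| Poisson, 1.5/yr | 20.3% | 60.0% | +4.4 | +7.9 |
| Poisson, 1.0/yr | 34.6% | 69.4% | +3.9 | +7.0 |
| Poisson, 0.5/yr | 58.8% | 82.2% | +2.6 | +4.7 |
| Negative binomial k = 2, 0.5/yr | 69.6% | 85.7% | +1.8 | +3.2 |
| Poisson, rate set so that p = 80% | 80.0% | 91.8% | +1.3 | +2.4 |

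Worked line: at 1.0 per year with 45 dosed, 5 × (69.4 − 34.6)/45 = 3.9 points, so 34.6% is shown as 38.4%. At p = 80% with 50 dosed, 10 × (91.8 − 80.0)/50 = 2.4 points.

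The same formula applies to the bleed-free percentage, with bleeds in place of infusions. Protocol 9.2 assumes 1.5 total bleeds per year after infusion, which is the first row if bleeds are Poisson.

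**Resumption.** Assume 15% resume, evenly over 469 days. The extra participants have mean follow-up 455/2 = 227.5 days, so their average is 15% × 227.5/469 = 7.3%.

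- 45 dosed: (40 × 15 + 5 × 7.3)/45 = 14.1%, short by 5 × (0.150 − 0.073) = 0.4 participants.
- 50 dosed: (40 × 15 + 10 × 7.3)/50 = 13.5%, short by 0.8 participants.

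If resumption instead occurs only inside the window, the mean fraction of the window observed is 373²/(2 × 455 × 388) = 0.394 and the extra participants' average is 5.9%. The shown figures become 14.0% and 13.2%, short by 0.5 and 0.9 participants.

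**Bounds.** With 40 dosed, all at Month 15, every shift is zero. At the other extreme, which is not even accrual, suppose 50 are dosed and the last 10 have no window time. Then 24/40 = 60% infusion-free becomes 34/50 = 68%, and 6/40 = 15% resuming becomes 6/50 = 12%.

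**The case against.** **The SAP never says these participants count as successes.** True; a reader might infer that it does. SAP 5.2.1 bases binary summaries on observations that are not missing, and SAP 5.3 says missing data are generally not imputed. A participant not yet at Day 82 could reasonably be treated as missing. Under the accrual model, dropping only those participants cuts the 45-dosed shift at 1.0 per year from +3.9 to +2.6 points. But an incomplete window is never defined as missing, so a participant inside it still enters as event-free.

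**The Evaluable set excludes those not at Month 15.** It does, but the SAP uses it to repeat the main ABR, AIR and FIX:C analyses. SAP 6.2.2.2 (infusion-free) and 6.2.6 specify Dosed, and resumption falls under the Dosed default in Section 5.

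**The plan expects 40.** The protocol synopsis foresees about 50 screened to dose 40, so 50 dosed would need no screen failures or more screening than planned. This weakens the top of the range. It does not remove the case, because Protocol 9.2 expressly allows more than 40.

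**The larger shifts rest on low infusion-free percentages.** Agreed. In the Phase 1/2 study (Protocol 2.2.2), 8 of 10 participants used no factor. That is a small study with different follow-up, but at 80% the shift is only +1.3 or +2.4 points.

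**Resumption is captured elsewhere.** The protocol's estimand text assesses it through AIR and FIX consumption, both annualised. Calling the resumption percentage the trial's direct measure of treatment failure would go beyond the documents.

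**Conclusion.** The point holds, conditionally. It arises only if more than 40 are dosed and some have not completed the window at the data cutoff. The Dosed-population rule, followed as written, then overstates the bleed-free and infusion-free percentages and understates resumption.

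Under even accrual and the event rates assumed above, the infusion-free shift is about 1 to 4 points with 45 dosed and 2 to 8 points with 50. Resumption at an assumed 15% is understated by less than one participant.

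A reader might infer that the primary result is compromised. The documents do not support that. None of the three percentages is in the gatekeeping sequence (SAP 5.1, Table 2), and the SAP plans only descriptive summaries for them. The primary test on total bleeds uses annualised data, so neither it nor its type I error is touched. This is a low-cost clarification, worth making because the direction favours the product.

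**What to change.** In SAP 6.2.2.2 and 6.2.6, state that at the primary analysis the Week 12 to Month 15 percentages use as denominator the participants dosed at least 469 days before the data cutoff, with early withdrawals and resumers kept in. Covering both sections keeps the bleed-free and infusion-free percentages on one denominator. For resumption, also report the Kaplan-Meier proportion by Month 15 in all dosed participants, whether or not the 20% condition is met.

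The cost is a sentence in each section, a denominator flag and one estimate. The jump-to-reference analysis in SAP 6.1.1.2 already selects on time from dosing to data cutoff, so the flag is close to one already needed. The downside is that a few participants are left out of these percentages until the next data cut. The flag does not deal with those who withdraw early while event-free; showing their number beside each percentage would make that visible.
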